Although 83% of U.S. households now have smoke free home rules, only 46% of households with smokers have bans, and just 37% of households with low-income smokers have them. We hypothesize that expanding population-level cessation services to include Smoke Free Homes will engage more low-income smokers in proven interventions and yield greater cessation than current standard practice. Our proposed approach is based on six broad claims supported by strong evidence from multiple disciplines:

1. Most low-income smokers are not ready to quit. Readiness to quit is the strongest predictor of making a quit attempt. Compared to smokers not thinking about quitting, those planning to quit in the next 30 days are six times more likely to try quitting and four times more likely to succeed. But low-income and low-education smokers are significantly less likely to be planning to quit. Studies in diverse populations and settings consistently find that only 20-30% of low-income smokers are ready to quit in the next 30 days. In current standard practice, these smokers are ineligible to receive cessation services and offered nothing to help them prepare to quit. NCI's Tobacco Control Research Priorities for 2016-2025 call for interventions that "reach and engage" ambivalent smokers and facilitate "transition from unmotivated smoker to abstinence" (Priority 6-2).

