Aim 1 will use intention-to-treat analyses, providing the most conservative estimate of intervention effects. With randomization and a large sample, we expect baseline characteristics to be similar by group. We will test for this using t-tests for continuous variables and chi-square tests for categorical variables. If significant differences are found, we will include those variables as covariates in all analyses. For Aim 1A (abstinence from smoking) the Cochran-Mantel-Haenszel test will be used to test the conditional association between study group and abstinence at 3- and 6-month follow-up, controlling for states. A Breslow-Day test will be used to examine whether there is a common odds ratio (OR) across states. Finding greater odds of abstinence across states for the group receiving both Quitline and Smoke Free Homes would support the hypothesized intervention effects. If the Breslow-Day test is significant, we will estimate state-specific ORs. To control for other potential covariates, we will regress abstinence at 3- and 6-month follow-up on study group and other covariates using logistic regression. In the regression model, 8 dummy variables for states will be created to account for differences in state Quitlines. Adjusted odds ratios (OR) and 95% confidence intervals (CI) will be reported to quantify the associations. Study group effects for Aim 1B (made a quit attempt or did not) will be examined in a series of analyses similar to those described for Aim 1A. Finding a greater odds of quit attempts in the Quitline and Smoke Free Homes group across states would support hypothesized effects. For Aim 1C, cigarettes smoked per day is a count dependent variable (DV) measured at baseline, 3- and 6-month follow-up and assumed to follow the Poisson distribution. If the assumption of Poisson distribution is met, we will regress the DV on study group, states and other potential covariates and allow the  $\beta$  for study group as a random effect using random-effect Poisson regression. Otherwise, we will fit random effect negative binomial regression to the data. Finding a larger decrease in cigarettes smoked per day in the combined group (vs. Quitline alone) would support the hypothesized effect. Analyses for Aim 1D will replicate those for Aims 1A-C, but be conducted in only the subset of participants from both groups who declined quitline services when offered at baseline. Regression analyses for Aim 1D will also test baseline variables described previously (see "Baseline survey"), because quitline acceptance rates may differ by group. These comparisons provide the best estimate of the added benefit of offering Smoke Free Homes to smokers who are not yet ready to quit.

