
**Aim 2.** The primary implementation research question in this Hybrid Type 2 trial is whether demand for and engagement in quitline services – operationalized as acceptance and use – differs by study group. In Aim 2A, the DV is dichotomous (accepts Quitline/does not). Using the same analytical strategies and statistical methods described for Aim 1A, we will examine cumulative probabilities of accepting quitline services during the study period by group, adjusting for baseline covariates. Finding a greater likelihood of accepting quitline services in the combined group (vs. Quitline only) will support our hypothesis. For Aim 2B, the DV is whether participants use 0, 1 or 2+ quitline counseling sessions, and will be treated as an ordinal variable. Counseling sessions include all inbound and outbound phone interactions between a quit coach and participant. Among those who accept quitline services, we will regress number of quitline sessions used by the end of the study on study group and other baseline measures using ordinal logistic regression. The proportional odds assumption will be tested using the score chisquare test. If it is met, adjusted ORs and 95% CIs will be reported from the ordinal logistic regression model. Otherwise, multinomial logistic regression will be used to compare different probabilities (e.g., 0 vs 1 and 0 vs 2+ sessions), adjusting for potential baseline covariates. Finding greater odds of using more sessions in the Quitline and Smoke Free Homes group will support our hypothesis. Aim 2C examines our hypothesis that integrating a Smoke Free Homes intervention into an existing tobacco treatment system will move smokers who are not yet ready to quit incrementally closer to quitting. Readiness to quit, pessimism about quitting and ambivalence about smoking are continuous DVs for this aim. Among participants still smoking at the end of the study, the level of readiness, pessimism and ambivalence at 6-month follow-up will be regressed on study group, states, baseline DV and baseline

characteristics using ordinary least square regression. Finding greater readiness to quit, greater ambivalence about smoking, and less pessimism about quitting in the Quitline and Smoke Free Homes group (vs. Quitline only) would support our hypothesis.

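### Covariates for the abstinence analysis are selected by baseline significance tests, and no text assures baseline readiness to quit a place in the primary model

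*Combined protocol and SAP*

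**What the plan says.** Section 1.20, Aim 1, expects the arms to be balanced and then checks it: "We will test for this using t-tests for continuous variables and chi-square tests for categorical variables". The consequence of a positive test follows: "If significant differences are found, we will include those variables as covariates in all analyses".

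For Aim 1A, "the Cochran-Mantel-Haenszel test will be used to test the conditional association between study group and abstinence", with state as the stratifying factor. A regression is then added: "To control for other potential covariates, we will regress abstinence at 3- and 6-month follow-up on study group and other covariates using logistic regression". The only covariates named for it are the state indicators: "8 dummy variables for states will be created to account for differences in state Quitlines". Aim 1B follows the same scheme, and Aim 1C refers in the same general way to further covariates.

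Other aims go further. Aim 1D also examines the baseline survey variables. Aims 2A and 2B adjust for baseline measures. In Aim 2C each belief score is "regressed on study group, states, baseline DV" and baseline characteristics. Readiness is one of those scores, so it is collected at baseline.

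Section 1.5, claim 1, ranks readiness above other predictors of a quit attempt. It reports that "those planning to quit in the next 30 days are six times more likely to try quitting and four times more likely to succeed". The reference group for that statement is people who have no thought of giving up.

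**The concern.** Under randomisation, a significant baseline difference is a chance event. Its p-value carries no information on whether the variable predicts quitting. A rule built on it can bring in an irrelevant variable and pass over a strong predictor whose imbalance falls short of significance.

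The regression on further covariates does not close the gap, because it gives neither a list nor a selection rule. The adjustment set for the primary outcome can still be settled after the data are seen.

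There is also a practical difficulty. The rule is to apply throughout, yet the Aim 1A test is described as controlling for state alone. If a variable tests significant, the plan does not say whether it becomes an extra stratum, is left to the regression, or changes which result is the headline. The two analyses can give different answers, and neither is named as primary.

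**Working it through.** **Inputs.**
- Section 1.21: quit rates of 6% and 11%, 558 per group at 85% power, 1,980 enrolled, 40% attrition.
- Section 1.5: 20–30% of low-income smokers ready to quit in 30 days; four-fold success ratio.
- Assumptions: two-sided alpha of 0.05 for the design and for the baseline tests (neither is stated), and 5 to 20 independent baseline tests (no count is given).

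**The plan's own figure.** With pooled variance and no continuity correction, n = [z(0.975)·√(2·p̄·(1−p̄)) + z(0.85)·√(p₁(1−p₁)+p₂(1−p₂))]² / (p₂−p₁)². With p̄ = 0.085:
- 1.960 × √0.15555 = 0.773
- 1.036 × √0.1543 = 0.407
- (0.773 + 0.407)² / 0.0025 ≈ 557, rounded up to 558.

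Power at 558 per group is 85.1%. The enrolment figure also agrees: 1,980 × 0.60 = 1,188 completers, or 594 per arm. The sample size reproduces and is not in dispute.

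**How often the screen admits something.** At the 0.05 level, readiness passes in about 5% of trials (simulated 4.7–5.4%). Under this rule alone it is left out of about 95%. The probability that at least one of k independent variables enters by chance is 1 − 0.95^k:

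| k | At least one enters | Expected number |
|---|---|---|
| 5 | 23% | 0.25 |
| 10 | 40% | 0.5 |
| 15 | 54% | 0.75 |
| 20 | 64% | 1 |

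**Power.** Trials were simulated with 558 per arm, ready smokers four times as likely to quit, and 6% against 11% overall. Control quit rates follow from the overall 6%:
- 20% ready: 0.06 / (0.8 + 0.2 × 4) = 3.75% if not ready, 15% if ready.
- 30% ready: 0.06 / (0.7 + 0.3 × 4) = 3.2% if not ready, 12.6% if ready.

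The treatment effect was a common odds ratio set to give 11% overall. State strata were left out. Each scenario had 6,000 trials, analysed by logistic regression.

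| Handling of readiness | 20% ready | 30% ready |
|---|---|---|
| Never included | 85.4% | 85.4% |
| Only if significant at baseline | 85.7% | 85.7% |
| Always included | 87.0% | 86.9% |

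The gain over the screening rule is 87.0 − 85.7 = 1.3 points and 86.9 − 85.7 = 1.2 points. The Monte Carlo standard error of each rate is √(0.86 × 0.14 / 6,000) ≈ 0.45 points. The methods are compared on the same simulated trials, so the differences are more precise than that. A separate run at 594 per arm, with 400,000 trials per scenario and a readiness-stratified test as the adjusted analysis, gave about 87.8% under the rule and 89.1% with readiness always included. That is a gain of the same size.

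**Type I error.** With no treatment effect (6% or 11% in both arms, 20,000 trials each), the two-sided error was 4.5–5.2% under all three approaches.

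**The case against.** Several stronger readings are tempting, and the documents do not support them.

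- **Readiness is excluded unless it differs by chance.** The plan says that significant variables go in. It does not say that others stay out, and the logistic regression on further covariates could include readiness. What the text shows is that its inclusion is not assured.
- **Chance differences drive the model.** State is always in the analysis, the named Aim 1A test is stratified by state, and Aims 1D and 2 use baseline variables more widely. The screen looks at baseline data, not outcomes.
- **The rule produces false positives.** In roughly 12–16% of null trials there is a non-significant readiness imbalance of more than 2.5 points favouring Arm 2. In those, a false claim for Arm 2 occurs in about 4% without adjustment and about 2.5% with it. This is a conditional figure. It is worth about 0.14 × (4.1 − 2.5) ≈ 0.2 points of one-sided error overall, and trials with the opposite imbalance offset it.
- **The Cochran-Mantel-Haenszel test cannot take other covariates.** It can be stratified on further categorical factors. The fair criticism is that the plan describes it as controlling for state and does not say how an added covariate would be handled.
- **Adjustment gives free precision.** In logistic regression a prognostic covariate does not shrink the standard error of the log odds ratio. The estimate becomes a conditional odds ratio, generally further from 1, and the benefit is a small gain in power.

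The size of that gain is also open to challenge. The four-fold ratio compares ready smokers with those not thinking about quitting, whereas the simulation applies it to ready smokers against everyone else. These points limit the concern. They leave standing the choice of covariates by significance, the missing list and the unnamed primary analysis.

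**Conclusion.** The concern holds as a gap in pre-specification with a modest cost. The one stated selection rule for Aims 1A to 1C uses chance imbalance, and the alternative route is undefined. As a result, a predictor the plan itself ranks first, and already collects, is not secured for the primary abstinence model. How the rule applies to the state-stratified test, and which analysis is primary, are left open.

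The loss is about 1 to 1.5 points of power, probably an upper figure, with no inflation of overall type I error. This rests on a two-sided 0.05 level, 20–30% ready, and a four-fold ratio between ready and all other smokers. The 23–64% range rests on an assumed 5 to 20 independent baseline tests. The validity of the trial is not threatened, but the change is worth making because it removes an open choice on the primary outcome at almost no cost.

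**What to change.** In section 1.20:

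1. Delete the baseline significance tests and the rule that adds significant variables. Show baseline balance descriptively.
2. For 6-month abstinence, and for Aim 1B, pre-specify a logistic regression on study group, state, baseline readiness and baseline cigarettes per day, used whatever balance is observed.
3. State in advance whether this model or the state-stratified Cochran-Mantel-Haenszel test is primary. The other is then supportive.
4. For Aim 1C, add baseline readiness. Treat baseline cigarettes per day either as one of the repeated outcome measurements or as a covariate, not both.
5. Do not impose one fixed set on every aim. Keep the wider baseline set in Aim 1D, where quitline acceptance may differ by group, and the baseline value of each outcome in Aim 2C. Name each set in advance.

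The cost is SAP wording only: readiness and cigarettes per day are already measured at baseline, and no participants or visits are added. The one downside is interpretive. The adjusted odds ratio is conditional on the covariates and should be labelled so, because it need not equal the odds ratio stratified by state alone.

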The intervention is a Hybrid Type 2 design, which means that we will compare the standard practice intervention (the state Quitline; Arm 1) with the expanded service alternative (the Quitline in addition to Smoke-Free Homes; Arm 2) among 1,980 low-income smokers across nine states. Participants will be randomly assigned to each Study Arm. The study outcomes are 7-day and 30-day point prevalence of smoking abstinence, number of cigarettes per day, number of 24-hour quit attempts, and acceptance of the interventions. Participants will be recruited from nine state United Way 2-1-1 agencies. The Quitline (standard service) will be delivered by our study partner Optum, a health-care services company that runs the state Quitlines. 2-1-1 callers who are daily smokers and interested in participating will be contacted by our study team who will conduct surveys by telephone with participants at Baseline, 3-month follow-up, and 6-month followup.

**1.4** Specify your research question(s), study aims or hypotheses:
 

**Aim 1:** Compare quit rates in Quitline only vs. Quitline + Smoke-Free Homes groups

- A. What proportion report 7-day and 30-day point prevalence abstinence at 3- and 6-month follow-up?
- B. What proportion report making a quit attempt (of at least 24 hours) at 3- and 6-month follow-up?
- C. What is the average change in cigarettes smoked per day at 3- and 6-month follow-up?
- D. Among those who decline Quitline services at baseline, what proportion report abstinence, quit attempts, and decrease in cigarettes smoked per day at 3- and 6-month follow-up?

**Aim 2:** Compare acceptance and use of Quitline services, and pro-cessation beliefs cumulatively over the study period in Quitline only vs. Quitline + Smoke-Free Homes groups.

- A. What proportion accept Quitline services?
- B. Among those who accept Quitline services, what proportion use 0, 1, or 2+ sessions of counseling?
- C. Among those still smoking at 6-month follow-up, how does readiness to quit, pessimism about quitting, and ambivalence about smoking differ by group?

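### Aim 1C targets a change in cigarettes per day, but its model names no time, group-by-time or baseline-value term; if baseline rows are outcomes, the group coefficient understates the average follow-up difference

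*Combined protocol and SAP*

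**What the plan says.** Item 1.4 frames Aim 1C as "What is the average change in cigarettes smoked per day at 3- and 6-month follow-up". Item 1.20 describes the outcome: "cigarettes smoked per day is a count dependent variable (DV) measured at baseline, 3- and 6-month follow-up". For the model it says "we will regress the DV on study group, states and other potential covariates", with the coefficient "for study group as a random effect using random-effect Poisson regression". The level at which that coefficient varies is not given. The negative binomial fallback adds no terms. The success rule is: "Finding a larger decrease in cigarettes smoked per day in the combined group (vs. Quitline alone) would support the hypothesized effect".

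Under the general Aim 1 rule, a baseline variable becomes a covariate when it differs significantly between arms. For the quitline decliners, "Analyses for Aim 1D will replicate those for Aims 1A-C", and "Regression analyses for Aim 1D will also test baseline variables described previously". By contrast, Aim 2C models the 6-month value, "regressed on study group, states, baseline DV" and baseline characteristics.

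**The concern.** The aim and its success rule are about a difference in change between arms. The named terms contain nothing that expresses change. With three measurements per person and a random-effect model, the natural (though not the only) reading is that all three are rows of the outcome. Randomised arms have no expected difference at baseline, so one group coefficient fitted across the three rows is pulled toward zero.

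A single coefficient also cannot give the separate 3- and 6-month answers that item 1.4 asks for. What is at stake is the reported size of a secondary effect, which a reader could take as a smaller reduction in smoking than occurred.

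**Working it through.** **The plan's own figures.** Item 1.21 gives no sample size or power for Aim 1C. Its figure for the primary outcome (6% vs 11%, 558 per group, 85% power) reproduces: 558 per arm and 85.1% power, assuming two-sided 0.05. It does not depend on this point.

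**Inputs from the documents.** Effect of -2.9 per day (item 1.5, earlier Smoke-Free Homes trials). A smaller effect of 2.9 × 0.75 × 0.65 = 1.4 per day, using item 1.21: 75% decline the quitline and 65% of those accept Smoke-Free Homes. Follow-up of 73% and 60% (item 1.5, ongoing trial); item 1.21 also expects 40% attrition at 6 months.

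**Assumed.** Baseline mean of 14 cigarettes per day; control follow-up mean equal to a fraction f = 0.75 to 1 of baseline; dropout unrelated to smoking.

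**Closed form, no time term, equal effects at both visits.** Let r be the sum of the two follow-up proportions and R the true rate ratio. The group rate ratio is (1 + r·f·R)/(1 + r·f).

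| r | f | Effect per day | R | True log ratio | Model log ratio | Kept |
|---|---|---|---|---|---|---|
| 1.33 | 1 | -1.4 | 0.900 | -0.105 | -0.059 | 56% |
| 1.33 | 0.75 | -1.4 | 0.867 | -0.143 | -0.069 | 48% |
| 1.33 | 0.75 | -2.9 | 0.724 | -0.323 | -0.148 | 46% |

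With complete data (r = 2) the same three rows keep 65%, 58% and 56%.

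**Fits to simulated data.** Random-intercept Poisson models were fitted by maximum likelihood under two sets of assumptions: (a) normal intercepts, log SD 0.3 and 0.5, baseline mean 14; (b) gamma intercepts, shape 4, baseline means 10, 15 and 20. State terms were omitted.

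| Terms | Follow-up | (a) | (b) |
|---|---|---|---|
| Group only | 73%/60% | 39-48% | 37-45% |
| Group only | complete | 55-63% | 56-62% |
| Group + time | 73%/60% | 40-48% | 39-46% |
| Group + log baseline, baseline rows kept | 73%/60% | 45-54% | not run |
| Group-by-time contrast | 73%/60% | 95-104% | 96-101% |
| 6-month value with log baseline as covariate | 73%/60% | 95-103% | not run |

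The fits at 73%/60% fall below the closed form because people seen only at baseline contribute a zero difference. A time main effect alone does not cure the dilution. Nor does a baseline covariate while the baseline rows stay in, so the extra baseline variables in Aim 1D do not either. Study group is constant within a participant, so a random coefficient on it adds no time contrast.

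**Unequal effects, judged against 6 months.** Closed form, 6-month effect -1.4:

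- Half the effect at 3 months, f = 1, 73%/60%: (1 + 0.73 × 0.95 + 0.60 × 0.90)/2.33 = 0.959, log -0.042, 40% kept.
- Fading by a ratio of 1.9, f = 1, 73%/60%: (1 + 0.73 × 0.81 + 0.60 × 0.90)/2.33 = 0.915, log -0.089, 85% kept. At f = 0.75 it is 73%. With complete data it is 86-96%.
- 3-month effect twice the 6-month effect, f = 1, complete data: (1 + 0.80 + 0.90)/3 = 0.900, which equals the true 6-month ratio. A steeper fade would overstate the 6-month contrast.

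**The case against.** The strongest reply is that the dilution belongs to one reading. Item 1.20 is a summary in an ethics application, and listing baseline may only describe when data are collected. A time-free model with baseline rows cannot express a decrease, so the success rule itself argues against that reading. This stands: a reader might infer that the plan certainly yields a biased estimate, and the text does not support that. The follow-up-only reading is not a full answer, however. It removes the dilution but compares levels, with no commitment to use the baseline count.

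Second, the percentages come from participant-intercept models, whereas the plan names a random coefficient on group and no participant intercept. They also rest on assumed means, variance and dropout. This stands too, so they show rough size only.

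Third, a reader might call the error simply conservative. That is too firm. In the North Carolina trial in item 1.5 the home-ban difference fell from 19 points (38% vs 19%) to 10 (43% vs 33%), which is the source of the 1.9 ratio above. It is a proxy, since it concerns bans and not cigarettes, but it shows that fading is plausible. In Aim 1D the subset is defined after randomisation and the plan allows that quitline acceptance may differ by group. The arms may then differ at baseline, and the direction is not guaranteed.

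Fourth, item 1.11 asks at 3 months for the count among those who still smoke. A reader might infer that abstainers are dropped from Aim 1C. That is a survey routing, not an analysis exclusion, and Aim 1 is stated to be intention-to-treat.

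**Conclusion.** The point holds as a specification gap with a conditional consequence. If baseline rows are part of the outcome, the Aim 1C group coefficient understates the average follow-up difference. With equal effects at 3 and 6 months it keeps very roughly 40-65% of the log rate ratio, given the assumed means, variance and dropout. Relative to 6 months alone, the shortfall shrinks with a fading effect and could reverse beyond about a twofold fade. If only follow-up rows are outcomes, nothing is diluted, but an available baseline adjustment is left unnamed.

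Neither lost power nor inflated false positives should be read into this: power depends on variances that the documents do not give, and no false-positive problem arises with a participant intercept. The level of the random coefficient and the handling of abstainers are clarifications only.

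**What to change.** In item 1.20, specify one of two models for Aim 1C:

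1. A participant random intercept with fixed effects for group, time (baseline, 3 and 6 months), group-by-time and state, reporting the 3- and 6-month group-by-time contrasts.
2. Follow-up cigarettes per day as the outcome, with baseline cigarettes per day as a covariate, as Aim 2C does for its own outcomes.

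Use negative binomial if the counts are overdispersed, and the same model in Aim 1D. State the level (participant or state) of any random study-group coefficient. State whether abstainers enter as 0, which fits the intention-to-treat statement; leaving them out would answer a question about continuing smokers only.

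The cost is a few sentences of analysis text, using data already planned for collection.

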 Based on previous research, in both groups, 25% of participants will accept QL when offered (Pilot 1, ongoing cessation R01); 42%, 31% and 27% will take 0, 1 and 2+ QL calls, respectively (ongoing cessation R01); and 12%, 13% and 31% will report quitting, respectively (ongoing cessation R01). In the QL+SFH group, 65% of those who decline QL will accept SFH (Pilot 2, SFH trials); of those accepting, 37% will create a SFH and 63% will not, with corresponding quit rates of 26% and 5% (SFH trials). We assume all who decline QL and SFH will quit at a very low rate (2%). Using these data to estimate cessation after a first offer of QL and SFH yields intent-to-treat quit rates of 5.9% (SFH) and 11% (QL+SFH). Even if no other cessation occurs, the study is powered to detect this difference. If we assume the same intervention use and quit rates apply for a second offer of QL and SFH (at 3-month follow-up), intent-to-treat quit rates would be 9.6% (SFH) and 17.5% (QL+SFH), also within the study's power. We are confident that the final quit rates for each group will fall between these values.

We used G\*Power to calculate the sample size required to detect study group quit rate differences of 6 vs 11% (minimum expected), 8 vs 14%, and 10 vs 17% (maximum expected) at three levels of power. As shown, with 1,116 participants (558 per group) completing 6-month follow-up, we can detect a 6 vs 11% difference with 85% power. Power will be greater for larger differences. Attrition is expected to be 40% at 6-month follow-up, thus a baseline sample of 1,980 assures enough participants at follow-up (n=1,188) even if attrition is slightly higher than projected.

**1.23** Will any data from this project be stored for use in future research studies?  
 Yes - contribution for future use is mandatory for participation in the study

**1.24** Does this project involve the collection or use of biological samples or genetic data?  
 No

**1.25** Are you requesting institutional certification to contribute human data or samples to a repository or database for broad sharing (public or restricted access)?  
 No

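### Aim 1D fits ordinary logistic regression to between about 49 and 96 expected quits at 6 months, which modestly overstates the adjusted odds ratio; Firth's penalised likelihood would remove nearly all of that bias

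*Combined protocol and SAP*

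**What the plan says.** Section 1.20 defines Aim 1D as a repeat of Aims 1A to 1C, restricted to participants in both arms who declined the quitline when it was offered at baseline. For abstinence this brings over three things from Aim 1A: a Cochran-Mantel-Haenszel test stratified by state; a Breslow-Day test that leads to state-specific odds ratios if significant; and a logistic regression in which "8 dummy variables for states will be created to account for differences in state Quitlines". For the subset it adds: "Regression analyses for Aim 1D will also test baseline variables described previously". The stated reason is that quitline acceptance may differ by arm. No penalised or exact method, covariate limit or event count is given.

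The section then says of the Aim 1D analyses as a whole: "These comparisons provide the best estimate of the added benefit of offering Smoke Free Homes".

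Section 1.21 gives the inputs from which the number of quits in this subset can be worked out. It does not work it out.

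**The concern.** Maximum-likelihood logistic regression is biased away from an odds ratio of 1 when events are few relative to the number of coefficients. Restricting to decliners removes the participants with the highest assumed quit rates, and the control arm of the subset is left with very few quits. The model still carries eight state terms, to which baseline variables are added. The bias runs in the direction the study hopes to find, in a set of analyses to which the plan gives special weight. A few missing control quits can also leave a state-specific odds ratio without a finite estimate.

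**Working it through.** **Reproducing the plan's figures (section 1.21).** The acceptance input is "in both groups, 25% of participants will accept QL when offered". Among accepters, "42%, 31% and 27% will take 0, 1 and 2+ QL calls, respectively", with quit rates of 12%, 13% and 31%.

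- Accepters' quit rate: 0.42 × 0.12 + 0.31 × 0.13 + 0.27 × 0.31 = 17.44%.
- Decliners, control arm: 2%.
- Decliners, combined arm: 0.65 × (0.37 × 0.26 + 0.63 × 0.05) + 0.35 × 0.02 = 9.00%.
- Whole control arm: 0.25 × 17.44% + 0.75 × 2% = 5.86%, the plan's 5.9% (printed there with the label SFH, where the quitline-only arm is evidently meant).
- Whole combined arm: 0.25 × 17.44% + 0.75 × 9.00% = 11.1%, the plan's 11%.
- Sample size for 6% versus 11% at 85% power (two-sided 0.05 assumed, pooled variance, no continuity correction): 558 per group, as stated.

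**Quits in the subset at 6 months, first offer only.** Completers: 1,980 × 0.60 = 1,188, or 594 per arm. Decliners: 594 × 0.75 = 445.5 per arm, assuming equal attrition in decliners and accepters. Quits: 445.5 × 2% = 8.9 and 445.5 × 9.00% = 40.1, total 49. The marginal odds ratio is 4.85.

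**With the second offer.** The plan's 9.6% and 17.5% imply the fraction f of non-quitters who receive it:

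- Control: (0.096 − 0.0586) / (0.9414 × 0.0586) = 0.68.
- Combined: (0.175 − 0.1111) / (0.8889 × 0.1111) = 0.65.

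With f = 0.665, decliner rates become 0.02 + 0.98 × 0.665 × 0.0586 = 5.8% and 0.0900 + 0.91 × 0.665 × 0.1111 = 15.7%. Quits are 25.9 + 70.1 = 96, and the odds ratio is about 3.0.

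**At 3 months.** The second offer is made at this visit, so it cannot add quits. With 73% follow-up (section 1.5), there are 990 × 0.75 × 0.73 = 542 decliners per arm. First-offer rates give about 60 quits (11 control). The 3-month quit rates in section 1.5 (15.6% and 4.5%) give a combined-arm rate of 0.65 × (0.37 × 0.156 + 0.63 × 0.045) + 0.007 = 6.3%, hence 34 + 11 = 45 quits.

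**Events per coefficient (arm, 8 states, k covariates).** At 49 quits: 49/9 = 5.4 for k = 0, 49/19 = 2.6 for k = 10, 49/29 = 1.7 for k = 20. At 96 quits: 10.7, 5.1 and 3.3.

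**Simulation.** 446 per arm, nine equal states, each covariate with a log odds ratio of 0.2 per SD (assumed); 1,500 trials per row at 49 quits and 800 at 96. Bias is measured against the true covariate-adjusted odds ratio. Coverage is for the ordinary 95% interval.

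| Quits | k | True OR | Bias in log OR | OR multiplied by | SD of log OR | Coverage | Firth bias |
|---|---|---|---|---|---|---|---|
| 49 | 0 | 4.85 | +0.055 | 1.06 | 0.41 | 96.3% | −0.007 |
| 49 | 5 | 4.92 | +0.080 | 1.08 | 0.43 | 95.5% | −0.002 |
| 49 | 10 | 5.00 | +0.108 | 1.11 | 0.43 | 96.4% | −0.001 |
| 49 | 20 | 5.19 | +0.161 | 1.17 | 0.46 | 94.5% | −0.022 |
| 96 | 0 | 3.02 | +0.026 | 1.03 | 0.24 | 94.9% | +0.004 |
| 96 | 10 | 3.16 | +0.030 | 1.03 | 0.27 | 94.8% | −0.016 |
| 96 | 20 | 3.30 | +0.072 | 1.07 | 0.26 | 95.6% | −0.006 |

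No fit failed. With unequal state sizes (assumed) at 49 quits, inflation was about 10% for k = 10 and 19% for k = 20. Root-mean-square error of the log odds ratio fell under Firth from 0.449 to 0.398 (11%) and from 0.498 to 0.407 (18%). Across all settings run, the reduction was about 10% to 19% at 49 quits and 3% to 9% at 96. In the 3-month setting with 45 quits, inflation was about 5%, 6% and 13% for k = 0, 10 and 20.

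**States with no control quits (equal states, Poisson approximation).** exp(−8.9/9) = 37% of states at 9 control quits; exp(−25.9/9) = 6% at 26.

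**The case against.** Several stronger readings are tempting, and the documents do not support them.

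- **That 49 quits is what the plan expects at 6 months.** It is the floor. Section 1.21 expects final rates to lie between the first-offer and second-offer scenarios, and the second offer is a study procedure (section 1.11). Inflation at the upper end is only about 3% to 7%. This stands for the 6-month analysis but gives no relief at 3 months.
- **That the covariates are known to be many.** The baseline-survey list is not in the text, and testing variables need not mean keeping them all in one model. At 49 quits, 0.055 of the bias arises with no baseline covariates: about half of the total for k = 10 (0.055/0.108) and a third for k = 20 (0.055/0.161).
- **That the plan names the adjusted odds ratio its best estimate.** That phrase covers every Aim 1D comparison, including the stratified test, quit attempts and cigarettes per day.
- **That states with no quits at all would often break the model.** No state allocation is given. With equal states this happens in about 4% of trials at 49 quits (9 × exp(−49/9)). Such a state adds no information on the group effect, so its diverging coefficient does little harm to the odds ratio at issue.
- **That the inference is invalid.** The largest bias in the table, 0.16, is about a third of the standard deviation of 0.46, and coverage stays near nominal.

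The stratified analysis is already planned, so recommending it adds nothing. It is no cure either: the Mantel-Haenszel odds ratio was itself about 4% to 6% too high at 49 quits. Cutting the covariate list is a trade-off, not a clear gain, because those variables are there to adjust for selection into the subset.

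**Conclusion.** The point holds as a minor, inexpensive improvement. Aim 1D uses ordinary logistic regression with sparse events and no safeguard. The adjusted group odds ratio for abstinence would on average be roughly 6% to 20% too high at 49 quits and about 3% to 7% at 96. Firth's method had bias close to zero and lower root-mean-square error in every scenario simulated.

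These sizes rest on the plan's own quit and acceptance rates, equal allocation, attrition unrelated to quitline acceptance, and 0 to 20 covariates of modest strength. The covariate count matters most at the lower event count. The primary whole-arm comparison is not at issue here, and nothing in the documents suggests that Aim 1D tests or intervals would mislead.

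**What to change.** In section 1.20, state that the Aim 1D logistic models for abstinence at 3 and 6 months will be fitted by Firth's penalised likelihood with profile-likelihood intervals, keeping the state terms and the baseline variables. Add that, in this subset, no state-specific odds ratio will be reported for a state with no quits in one arm, whatever the Breslow-Day result.

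The cost is a sentence or two of plan text, a non-default software option and slight shrinkage of the estimate. Sample size, data collection and the primary analysis are unchanged.
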